Tool Revision History:

Version Number	Version Date	Summary of Revisions Made
0.1	20 Feb 2018	Original version

Introductory Clinical Trial for Measuring Patients Before, During, and After an Electrophysiology (EP) Procedure with a Novel, Body-Worn Sensor

Principal Investigator:	[name] [contact] Department of Medicine New York Medical Center Electrophysiology [name]
Additional Investigators:	N/A
NYULMC Study Number:	S17-01618
ClinicalTrials.gov	NCT03657134
Funding Sponsor:	N/A
IND/IDE Number:	CoVa™ 2 is a Class 2 medical device (K160899) that received 510(k) approval from the FDA in June 2017 for measurements of HR, HRV, RR, TEMP, FLUIDS, SV, and CO.
Regulatory Sponsor:	N/A
Study Product:	CoVa Monitoring System 2
Study Product Provider:	toSense, Inc.

Initial version: A

AE	Adverse Event/Adverse Experience
CFR	Code of Federal Regulations
CO	Cardiac Output
CoVa™ 2	CoVa™ Monitoring System 2
DHHS	Department of Health and Human Services
DSMB	Data and Safety Monitoring Board
ECG	Electrocardiogram Waveform
EP	Electrophysiology
FLUIDS	Thoracic Fluids Measured with Impedance
GCP	Good Clinical Practice
HR	Heart Rate
HRV	Heart Rate Variability
ICH	International Conference on Harmonisation
IRB	Institutional Review Board
ISM	Independent Safety Monitor
MOP	Manual of Procedures
N	Number (typically refers to participants)
NIH	National Institutes of Health
OHRP	Office for Human Research Protections
OHSR	Office of Human Subjects Research
PI	Principal Investigator
QA	Quality Assurance
QC	Quality Control
RR	Respiration Rate
SOP	Standard Operating Procedure
SV	Stroke Volume
TBI	Thoracic Bioimpedance Waveform

[figure not shown]
Study number:
Version:

Protocol Summary

Title	Introductory Clinical Trial for Measuring Patients Before, During, and After an EP Procedure with a Novel, Body-Worn Sensor
Short Title	NA
Brief Summary	Subjects will be consented to wear the CoVa™ 2 prior to, during, and after after an Electrophysiology Procedure. During this time, the system will measure the following parameters from subjects: HR, HRV, RR, TEMP, FLUIDS, SC, and CO. Data will be retrospectively analyzed to determine if the system effectively operates under these conditions, and can effectively monitor subjects and allow them to be discharged early from the hospital. Subjects will not be measured while transferred in and out of the operating room. Approximate sample size is 20 subjects.
Phase	N/A

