Current hospital monitoring typically involves manually measuring conventional vital signs—such as blood pressure, heart rate, respiration rate, temperature, and pulse oximetry—initially every 15 minutes and then every few hours. This entire suite of vital signs is necessary, as it is rare that a single parameter can predict patient decompensation; more often, especially with complex disease states, all the vital signs (and often even more parameters) are required. And while not overly complicated, this process can be time consuming and inefficient. A clinician (typically a nurse, although increasingly someone with less training) enters the patient's room, straps to the patient a blood pressure cuff (around the brachium), an oximeter (on the finger), a thermometer (in the ear), and sometimes ECG leads (affixed to the chest), takes a series of

measurements, and then removes these sensors. The entire process takes about 5-10 minutes. Often measurement values are simply written down and transcribed later. Moreover, measurement of more sophisticated parameters, or measurements made outside of the hospital, are rarely done. In the hospital setting, parameters like stroke volume and cardiac output are typically only made with highly invasive or complicated devices requiring specialty-trained technicians, such as a pulmonary-arterial catheter or Doppler ultrasound machine. Patients are almost never discharged early and measured in the home, as the devices and infrastructure to enact such protocols do not exist. The sensor used in this clinical trial, is a low-cost, easy-to-use, body-worn system that cures the deficiencies listed above. It will ultimately measure all vital signs, along with stroke volume, cardiac output, and fluids, non-invasively and from a single location on the patient's body. This sensor can be coupled to a cloud-based system for data analytics that generates timely, actionable information for clinical staff regardless of patient setting (e.g. in either the home or hospital). With such a system, patients could be discharged early or monitored at home to prevent readmissions. This may improve patient outcomes, since delays in recognition of a change in status often lead toward longer hospital stays and, in some cases, patient morbidity and mortality.

Name and Description of the Investigational Agent

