toSense's CoVa™ 2 features a body-worn Sensor, Gateway, and Web-based System. The Sensor perform measurements by non-invasively sensing and processing single-lead ECG and TBI waveforms. Algorithms on the device processes these two waveforms to measure HR, HRV, RR, TEMP, FLUIDS, SV, and CO.

The Sensor has a form factor similar to a conventional necklace, with the electronics built into its strands and base. To make a measurement, a pair of customized disposable Electrodes—each featuring two electrode regions—snaps into a magnetic interface on the backside of the base and then attaches to the patient's chest. The Sensor is typically used for measurement periods less than 5 minutes but can also be used for longer periods (e.g. several hours or days).

Using a Bluetooth™ transceiver, the Sensor wirelessly transmits measurement information from the patient to a Gateway, such as a tablet computer or mobile phone running the Android operating system. These systems receive information from the Sensor, and then forward it to the Web-based System through either a local-area network (e.g., network based on 802.11), or a wide-area cellular network (e.g. AT&T). The Web-based System displays information and can forward it to a third-party system through a web-services interface.

CoVa™ is FDA-cleared (K160899) for the measurements described above.

Clinical Data to Date

See attached documents.

Known Potential Risks

Electrodes placed on the body may cause a slight redness or irritation. In rare cases, there is an allergic reaction or sensitivity to the adhesive that is used to stick the electrode patch. However, the adhesive that is used is not unique to this study, and is used in many medical applications. Discomfort could also occur when the adhesive patches are removed.

Known Potential Benefits

Subjects involved in this study will receive additional monitoring and may be discharged from hospital earlier as a result.

Objectives and Purpose

Primary Objective

When used before, during, and after an EP procedure, CoVa™ 2 is able to successfully measure vital signs, waveforms, and hemodynamic parameters from patients, indicate the efficacy of the EP procedure, and show any signs of patient decompensation or complications. Related to this primary objective is the goal of answering the following questions: Can data generated by CoVa™ 2 allow patients to be discharged from the hospital relatively early and monitored at home?

Secondary Objectives (if applicable)

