In addition to the primary study objective, investigate the following questions: 1) can measurements made by the CoVa™ 2 (particularly stroke volume (SV), cardiac output (CO), fluid status, arrhythmia detection, and basic vital signs) be successfully made before, during, and after an EP procedure?; 2) is there correlation between CoVa™ 2-measured parameters (particularly volume status, heart rate and arrhythmia, SV, and CO) before, during, and after an EP procedure?; 3) does RF ablation during an EP procedure interfere with CoVa™ 2 measurements?; 4) does a 200-300 Joule shock during a DC cardioversion procedure interfere with CoVa™ 2 measurements?; and 5) is the CoVa™ 2's usability suitable for hospital clinicians?

Description of Study Design

Study subjects scheduled for an EP procedure who have signed an informed consent form (ICF) will be admitted to the study. Prior to the EP procedure (e.g. in a hospital room or operating room at NYU Medical Center), an employee of NYU will prep the subject's skin with an alcohol wipe, apply the CoVa™ 2 Sensor using a pair of disposable electrodes, connect it to the Gateway Device using Bluetooth®, and ensure that it is transmitting information from the CoVa™ 2 Sensor through the Gateway Device to the Cloud-based System. All transmitted information will be de-identified. All subjects will continue to be monitored with standard of care equipment.

Once this data pathway is verified, measurements will be made from the subject for a period of approximately 2 hours prior to the EP procedure. More specifically, measurements will be made continuously for a period of about 90 seconds, and then, as described above, information will be transferred from the CoVa™ 2 to the Gateway Device, and from the Gateway Device to the Cloud-based System. This process will take roughly 120 seconds. Once it is complete, this 'duty cycle' will be repeated for the duration of the 2-hour period, i.e. measurements will again commence for a period of about 90 seconds, and then paused for about 120 seconds while data is wirelessly transmitted as described above.

Measurements will be temporarily halted as the subject is moved into the operating room and prepped for the EP procedure. Prior to the procedure, the CoVa™ 2 sensor will be attached to an external power supply as described above. Once the procedure is started, measurements will be made in the same manner as described above.

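### CoVa 2 measures neither blood pressure nor oximetry, which the protocol's rationale counts among the vital signs needed to predict decompensation, and no use of the concurrent routine readings is stated, so conclusions from CoVa 2 data alone would be poorly supported.

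*Protocol*

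**What the plan says.** The section *Introduction, Background Information and Scientific Rationale* describes current monitoring as manual measurement of "conventional vital signs—such as blood pressure, heart rate, respiration rate, temperature, and pulse oximetry". It continues: "This entire suite of vital signs is necessary, as it is rare that a single parameter can predict patient decompensation"; and, after the semicolon, "more often, especially with complex disease states, all the vital signs (and often even more parameters) are required". It then calls the sensor a "body-worn system that cures the deficiencies listed above", and adds that the sensor will eventually measure all vital signs.

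*Name and Description of the Investigational Agent* says what the device does now: "Algorithms on the device processes these two waveforms to measure HR, HRV, RR, TEMP, FLUIDS, SV, and CO". The front page gives the same seven items as the cleared measurements. The Protocol Summary says "the system will measure the following parameters from subjects: HR, HRV, RR, TEMP, FLUIDS, SC, and CO" (SC stands where the other lists have SV).

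The *Primary Objective* asks CoVa 2 to measure vital signs, waveforms and hemodynamic parameters, to indicate the efficacy of the procedure, and to "show any signs of patient decompensation or complications". A linked question asks whether CoVa 2 data can allow early discharge. *Description of Study Design* has the manufacturer's scientists process CoVa 2 measurement information to prove or disprove that hypothesis. It also keeps all subjects on standard-of-care equipment. *Primary Study Endpoints* sets success at 50% or more of subjects able to leave relatively early if monitored with CoVa 2, as judged retrospectively.

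**The concern.** The rationale and the device description do not fit together. The rationale counts blood pressure and oximetry among the signs needed to predict decompensation. The device supplies neither, yet the primary objective claims any sign of decompensation and the endpoint rests on monitoring with that device.

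If the retrospective determination uses CoVa 2 data alone, a subject whose only warning was in blood pressure or oxygen saturation would show nothing in the data examined. The protocol names no other measurement against which such a miss would come to light. The trial could then report that CoVa 2 supports early discharge without having looked at two of the signs that its own introduction treats as needed.

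**Working it through.** The protocol states no figure to reproduce. The check sets the lists and the data flow side by side.

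**1. Named vital signs against device outputs**

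| Vital sign named in the introduction | CoVa 2 output? |
|---|---|
| Blood pressure | No |
| Heart rate | Yes (HR) |
| Respiration rate | Yes (RR) |
| Temperature | Yes (TEMP) |
| Pulse oximetry | No |

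Covered: 3 of 5. Not covered: 5 − 3 = 2. The device has 7 outputs, so 7 − 3 = 4 lie outside the named list: HRV, FLUIDS, SV and CO. The front page, the Protocol Summary and the device description agree that blood pressure and oximetry are absent.

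**2. Strength of the premise.** The first half of the sentence calls the whole suite necessary. The second half is qualified: all the signs are needed more often than not, especially in complex disease. It is background reasoning, not a study criterion. It adds that further parameters are often needed, but nowhere does the protocol say that SV, CO or FLUIDS can stand in for blood pressure or saturation.

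**3. Data used for the primary hypothesis.** *Description of Study Design* names CoVa 2 measurement information. The Visit 2 steps cover application, testing, measurement and removal of the CoVa 2 device only. *Data Collection and Management Responsibilities* is generic. Standard-of-care monitoring continues, but no section brings its readings into the study data.

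**4. Effect on the primary proportion.** With about 20 subjects, one subject is 1/20 = 5 percentage points, and the 50% criterion is 0.50 × 20 = 10 subjects. This is only the weight of one classification, whichever way it errs. The number of subjects with a sign confined to blood pressure or saturation is not given and cannot be derived. The protocol also states no rule that turns measurements into a judgement of dischargeable, so the net direction of error cannot be derived either.

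**The case against.** The strongest reply is that the introduction mainly argues against relying on a single parameter. CoVa 2 supplies seven, including three (SV, CO and FLUIDS) that go beyond routine vital signs. Whether that set suffices is the empirical question of an introductory study. This stands, and it rules out one tempting inference: that the decompensation and early-discharge questions cannot be answered at all. Two missing signs weaken a positive conclusion; they do not make the question unanswerable.

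A reader might also infer that the error must favour success, since fewer signs examined means fewer subjects held back. That would need a rule by which any abnormality counts against early discharge. The protocol has none and leaves the determination to a retrospective report.

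A third inference is that listing "fluid status, arrhythmia detection, and basic vital signs" among the CoVa 2 measurements in the secondary objectives contradicts the device description, which has no arrhythmia output. It does not: the sensor records a single-lead ECG, and the primary objective includes waveforms.

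Two further replies stand in part. All-vital-signs measurement is presented as a future capability, which softens the conflict but confirms that the version under test lacks it. The deficiencies said to be cured can be read as the manual, slow and hospital-bound nature of current monitoring, so that phrase alone proves little. Finally, the choice of charted variables for the report could be left to a statistical analysis plan, which is not at hand, and the protocol does not say that CoVa 2 data are used exclusively. But an analysis plan can use only what is collected, and the reach of the primary objective is a matter for the protocol.

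**Conclusion.** The point holds in a limited form. By the protocol's own rationale, CoVa 2 lacks 2 of the 5 vital signs it names, and no use of the concurrent standard-of-care readings is stated. A conclusion drawn from CoVa 2 data alone, either that the device shows any sign of decompensation or that at least 50% of subjects could be discharged early, would be poorly supported.

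This assumes that the determination is made from CoVa 2 data, as *Description of Study Design* indicates, and that no document outside the protocol brings in the charted readings. The size of the effect on the primary proportion is unknown. The change is an inexpensive improvement that gives the trial a check on missed decompensation; it does not show the design to be invalid.

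**What to change.** 1. Abstract the blood pressure and oximetry values already recorded in routine care during the CoVa 2 monitoring period. Alongside the primary proportion, report how many subjects judged dischargeable on CoVa 2 data had a charted blood pressure or oximetry abnormality, or a clinical complication, in that period. The investigators should define a charted abnormality before the data are examined.
2. Limit the primary objective and the conclusion to signs in the parameters that CoVa 2 measures: HR, HRV, RR, TEMP, FLUIDS, SV, CO and the ECG and TBI waveforms. Reconcile the introduction's statement on the necessary suite with the device description.

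The cost is a protocol wording change and modest chart abstraction for about 20 subjects. The claim becomes narrower, and the result may look less favourable. No extra measurement of subjects is needed, and clinical care does not change.

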Once the EP procedure is complete, the subject will be transferred from the operating room to a hospital room, where they will stay overnight. Measurements will be made during this period, but not while the subject is being transferred. Once the subject is situated in the hospital room, the CoVa™ 2 Sensor will be applied to the subject and connected to the external power supply in the same manner as described above. Then measurements will commence according to the same duty cycle as described above.

The patient will continuously wear the CoVa™ 2 system until they are discharged for a period of about 24 hours. During this period, data from the sensor will be sent to the Gateway and Cloud-based System, and then analyzed retrospectively.

During the course of the study, scientists at toSense will use the Data Analytics Software to process measurement information from CoVa™ 2, with a focus of proving or disproving the study's primary hypothesis, i.e. when the CoVa™ 2 Sensor is used before, during, and after an EP procedure, can it successfully measure patients, indicate the efficacy of the EP procedure, show any signs of patient decompensation or complications, and allow a patient to be discharged relatively early?

More detailed analyses will investigate the study's secondary objectives, i.e.: 1) can measurements made by the CoVa™ 2 Sensor be successfully made before, during, and after an EP procedure; 2) is there correlation between parameters such as volume status, heart rate and arrhythmia, SV, and CO before, during, and after an EP procedure; 3) does RF ablation during an EP procedure interfere with CoVa™ 2 Sensor measurements?; 4) does a shock during a DC cardioversion interfere with CoVa™ 2 Sensor measurements?; and 5) is the usability of the CoVa™ 2 Sensor adequate before, during, and after an EP procedure suitable for clinicians?

Upon completion of the study, a report will be drafted describing the above-described information. The report may evolve into a peer-reviewed publication if this is determined by the PI to be an appropriate course of action.

This measurement protocol will be performed for a period of at approximately 6 months.

Study Endpoints

Primary Study Endpoints

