The primary endpoint will be if at least 50% of subjects studied in this trial are able to be discharged relatively early from the hospital if they are monitored with CoVa™ 2, as determined through a retrospective analysis. A detailed retrospective statistical report will be the determining factor in meeting this success criteria.

Study Enrollment and Withdrawal

Inclusion Criteria

In order to be eligible to participate in this study, an individual must meet all of the following criteria:

1. Patients with arrhythmias and other cardiac conditions that are scheduled for EP procedures.
2. Subject is over 22 years of age at the time of consenting
3. Subject and/or legally authorized representative is willing to undergo the informed consent process prior to enrollment in the study

Exclusion Criteria

An individual who meets any of the following criteria will be excluded from participation in this study:

1. Pregnant subjects
2. Subjects who are participating in another clinical study that may affect the results of either study

3. Subjects who are unwilling or unable to wear the sensor (and electrodes) for a period of up to 14 hours
4. Subjects who are considered by the principle investigator to be medically unsuitable for study participation

Vulnerable Subjects

Vulnerable subjects will not be utilized in this study. In the case of a vulnerable population patient being identified; they will not be included in the study or analysis..

Strategies for Recruitment and Retention

No NYULMC media will be used to recruit subjects. Subjects that are scheduled for an EP procedure and meet the inclusion criteria will be approached for enrollment.

Subjects will be consented in a quiet and private environment. Subjects will be given the opportunity to take the written consent form home to review overnight.

Use of DataCore/Epic Information for Recruitment Purposes

This study will utilize EPIC to identify subjects. Once potential subjects have been identified, the study team will notify the treating physician (TP) that they have patients eligible to participate. The study team will obtain approval from the treating physician to approach the eligible patient for the study.

Duration of Study Participation

The total duration of study participation is about 1.5 days. This includes:

Written Informed Consent Process: 1 day

Study Procedure: 1 day

Measurement prior to EP Procedure: 1-3 hours

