Measurement after EP procedure: Patient will be measured until they are discharged from hospital (approximately 24 hours).

Subjects may be contacted for a follow-up interview.

Total Number of Participants and Sites

This is a single-site study. Recruitment will end when approximately 20 participants are enrolled. It is expected that approximately 20-30 participants will be recruited in order to produce 20 evaluable participants.

Reasons for Withdrawal or Termination

Participants are free to withdraw from participation in the study at any time upon request. An investigator may terminate participation in the study if:

- Any clinical adverse event (AE), laboratory abnormality, or other medical condition or situation occurs such that continued participation in the study would not be in the best interest of the participant
- The participant meets an exclusion criterion (either newly developed or not previously recognized) that precludes further study participation

Handling of Participant Withdrawals or Termination

Withdraw criteria:

- The Principle Investigator will review whether a withdrawal of a subject affects the success criteria of the study. A subject may be replaced if it is determined that more subjects are needed based on this criterion

Premature Termination or Suspension of Study

This study may be temporarily suspended or prematurely terminated if there is sufficient reasonable cause. Written notification, documenting the reason for study suspension or termination. If the study is prematurely terminated or suspended, the PI will promptly inform the IRB and will provide the reason(s) for the termination or suspension.

Circumstances that may warrant termination or suspension include, but are not limited to:

- Determination of unexpected, significant, or unacceptable risk to participants
- Demonstration of efficacy that would warrant stopping
- Insufficient compliance to protocol requirements
- Data that are not sufficiently complete and/or evaluable
- Determination of futility

Study may resume once concerns about safety, protocol compliance, data quality are addressed and satisfy the IRB.

Study Agent (Study drug, device, biologic, vaccine etc.) and/or Procedural Intervention

Study Agent(s) and Control Description

Acquisition

toSense will ship CoVa™ 2 systems directly to the Electrophysiology supplies team at the NYU medical center.

New York Medical Center
[name],
[name]
New York, NY
10016

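### The only analyst the protocol names for the early-discharge question is the device maker, and who makes each subject's undefined, retrospective call is left open

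*Protocol*

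**What the plan says.** The Protocol, under Primary Study Endpoints, counts the trial a success if "at least 50% of subjects studied in this trial are able to be discharged relatively early from the hospital" when monitored with CoVa 2, as judged by retrospective analysis. It adds: "A detailed retrospective statistical report will be the determining factor in meeting this success criteria". No hours, reference time or clinical rule is attached to the term relatively early, either there or in the Protocol Summary.

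Description of Study Design says who works on the data and when. While the study is running, "scientists at toSense will use the Data Analytics Software to process measurement information from" CoVa 2, "with a focus of proving or disproving the study's primary hypothesis". The hypothesis as spelled out there includes whether the device can "allow a patient to be discharged relatively early". The firm is the provider of the study product; under Acquisition, "toSense will ship CoVa™ 2 systems directly to the Electrophysiology supplies team".

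The same section has subjects stay overnight after the procedure and wear the device until discharge at about 24 hours. It also says that a report will be drafted when the study is complete, without naming its author. The Methodology row of the Protocol Summary rules out blinding.

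**The concern.** Whether a subject could have left earlier is not observed in this design. It is a judgement reached afterwards, on a criterion the protocol does not define. The one party that the protocol assigns to analyse that question makes the device and so has an interest in the answer. No passage requires a clinician at the site to make or confirm the call, and no rule has to be fixed before data are seen.

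This is the trial's only stated primary endpoint. With about 20 subjects and a simple 50% line, a few borderline subjects read leniently could decide it. The exposure would exist even if all data were analysed once at the end. Processing during the study adds to it, because results could be known before the criterion is settled.

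**Working it through.** **What is assigned and what is not**

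| Step | Who, according to the Protocol |
|---|---|
| Process the readings to test the primary hypothesis, including early discharge | The device maker's scientists (Description of Study Design) |
| Define relatively early | Not stated |
| Classify each subject | Not stated; by retrospective analysis (Primary Study Endpoints) |
| Write the report that decides success | Not stated |
| Judge whether a withdrawal affects the success criteria | Principal investigator (Handling of Participant Withdrawals or Termination) |
| Hold the research data | The site's institution (Participant and Data Confidentiality) |

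**How sensitive the success rule is**

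The Protocol gives no error rate, power or expected discharge share, so there is no planned figure to reproduce.

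*From the Protocol:* 20 evaluable subjects (Total Number of Participants and Sites) and a threshold of 50%, that is 0.50 × 20 = 10 subjects.

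*Assumed:* a true share p of 0.30 or 0.40, and classification errors in the favourable direction only.

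Let X, the number truly able to leave early, be Binomial(20, p). With no misclassification, the chance of success is P(X ≥ 10). If k subjects are moved from not early to early, it becomes P(X ≥ 10 − k).

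| Subjects moved, k | Needed in truth | p = 0.30 | p = 0.40 |
|---|---|---|---|
| 0 | 10 | 0.048 | 0.245 |
| 1 | 9 | 0.113 | 0.404 |
| 2 | 8 | 0.228 | 0.584 |
| 3 | 7 | 0.392 | 0.750 |

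The same thing can be expressed as a proportion. If a share e of the subjects who are truly not early is called early, each subject is classified as early with probability q = p + (1 − p)e, and the chance of success is P(Y ≥ 10) with Y Binomial(20, q).

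| e | q at p = 0.30 | Chance | q at p = 0.40 | Chance |
|---|---|---|---|---|
| 0 | 0.30 | 0.048 | 0.40 | 0.245 |
| 0.1 | 0.37 | 0.165 | 0.46 | 0.444 |
| 0.2 | 0.44 | 0.374 | 0.52 | 0.657 |
| 0.3 | 0.51 | 0.623 | 0.58 | 0.830 |

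For example, at p = 0.40 and e = 0.2, q = 0.40 + 0.60 × 0.2 = 0.52.

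Both tables show how readily a 10-of-20 rule responds to a few reclassified subjects. They would look the same whoever did the reclassifying.

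**The case against.** The strongest reply is that the Protocol gives the maker data processing, not the verdict. A reader might infer that the maker's scientists classify the subjects and write the deciding report. The text does not say so: both tasks are unassigned, and the site has some part in the matter through the principal investigator's review of withdrawals and the storage of data at its institution. That inference should not be made.

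A reader might also see a slant in the aim given to the scientists. The phrase "with a focus of proving or disproving" names both outcomes and shows no intent to favour the device. The concern is about structure, not motive.

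Nor would handing the call to the site cure the problem. Site investigators are also unblinded, and without a definition their calls would be just as open. Much of the remedy's force therefore comes from fixing the definition. The change of classifier takes out the commercial interest only.

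The figures do not measure a bias caused by the maker. True shares and error rates are assumed, and errors run one way by construction.

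It could be added that a statistical analysis plan, not shown here, may name the analyst or adjudicator, and that Known Potential Benefits mentions possible earlier discharge as something subjects may gain. The first does not dispose of the point, because the maker's role, the endpoint wording and the deciding report are all set in the Protocol. Nor does the second, because the endpoint itself is determined in retrospect.

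Finally, the stakes are modest: this is a small, introductory, single-arm study in which subjects remain under standard monitoring. That bears on priority, not on whether the weakness is there.

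**Conclusion.** The point holds in a limited form. The Protocol gives analysis of the early-discharge question to the device maker during the study and names no other analyst of it. It lets a retrospective report decide success on a hypothetical, undefined call, and it leaves open who makes that call and who writes the report. The primary classification is therefore open to bias that site adjudication under a rule fixed in advance would reduce, though not remove.

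For scale only: with 20 subjects and a threshold of 10, two favourable reclassifications raise the chance of success from 24% to 58% at an assumed true share of 40%, and from 5% to 23% at 30%. These values rest on the assumed shares and on errors in one direction. The documents do not establish that such errors would occur or that the maker would make them. The change is worth making because it is cheap and protects the sole primary endpoint.

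**What to change.** Amend Description of Study Design and Primary Study Endpoints to state that:

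- the site investigators classify each subject as able or not able to be discharged early, under a written definition of relatively early. Its content is left to the investigators, and it is fixed before any subject's data are processed;
- they do so without sight of the maker's analyses of the hypothesis;
- the maker's part is limited to supplying processed readings from a version of the Data Analytics Software fixed at the same time;
- the report counts the site's classifications, and its author is named.

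The Key Roles section lists a principal investigator and a sub-investigator, while the title page gives no additional investigators. The amendment should settle who the classifiers are.

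The cost is protocol wording and a few hours of existing investigators' time for about 20 subjects. The hours are an estimate, not a figure from the Protocol. Some bias will remain because site staff are unblinded.
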